6.3.1. Bidirectional data exchange with existing national registries (LKR or equivalent)

A variety of registries exists, which aim to collect data on the disease course of cancer patients. Namely the registries on country basis (Landeskrebsregister) or clinical cancer registries of CCC's. For reporting institutions, it is tiresome to re-enter data on multiple platforms. Therefore, the GLA aims to establish an exchange strategy with the respective registries. Importantly, LKR's could serve to access all lymphoma patients diagnosed in Germany. The GLA-R could then approach individual sites to collect additional information on all patients or groups of special interest.

7. Research Projects within the Registry

7.1. Studies of Members of the GLA

In general, sites can retrieve the information about own patients entered into the registry in a condensed and automatized fashion. If further data/analysis are needed, each member of the GLA has the option to develop a distinct study to be conducted within the registry. An informal inquiry on a limited number of information, e.g. number of available patients and potential costs can be addressed to the managing group of the registry.

An appropriate study application should contain the scientific background, aims and endpoints of the research. All partners involved need to be declared as well as the role of a potential funding source. The application should name the responsible researchers, including the statistician, and describe the required data, the analysis plan and the intended use. The application template provided on the download section of the GLA-R homepage must be used. The application will undergo a central review process to address novelty, soundness and feasibility of the project as well as personal qualification

- The primary review will be performed by the respective working party, e.g. WP indolent lymphoma, aggressive lymphoma or biometry
 - The WP will judge the above-mentioned criteria
 - Will make a general recommendation and
 - Will recommend whether a project should centrally be funded by the GLA

- The secondary review will be performed by the steering committee (SC) of the registry. This review will focus on
 - Feasibility, financing and time lines and availability of resources
 - If there are several projects with WP approval the SC will prioritize work order and central funding of the projects
 - In addition, the steering committee will oversee the selection of authors to safeguard a fair distribution of authorships based on contribution to the respective work.

If there is a positive vote, the researcher may receive data sets for further analysis or a complete analysis as defined in the protocol of his project. Notwithstanding, approval of the project may not cover the costs of the project, however, the GLA can grant the conduct on excellent projects.

7.2. Collaboration with other study groups, legal institutions and commercial entities

Analyses of data within other scientific collaborators will always be an important way to fully exploit the data set obtained in the registry. This might occur in form of collaboration with other academic institution or groups or with commercial entities. Whatsoever, external partners must name a partner within the GLA, who will act as bailsman and will sponsor the project within the GLA.

7.2.1. Academic co-operations

The GLA-registry is open to share its data to the network of national and international academic databases. Whenever necessary, shared data analysis in order to address specific questions or to increase the power of distinct analysis will be performed. Data might be pooled in aggregated form or if necessary, on a patient level. In the latter case, data will be shared in an anonymized fashion, or (double) pseudonymized if indispensable for the work performed.

All these cooperative analyses will need approval of the WP/GLA-R steering committee, as described under 7.1. A contract or appropriate agreement needs to be signed by the involved project partners.

7.2.2. Cooperation with other partners, e.g. commercial entities

Besides the academic project collaborators, commercial entities (e.g. pharmaceutical companies) may ask to partner specific projects. This might be of benefit for patients, if the results can stimulate clinical projects or preclinical research to identify suitable treatment targets or access to treatment can be deemed, based on registry studies. Therefore, in general the GLA accepts to perform shared analysis with non-academic partners if the following criteria are fulfilled:

- The project is scientifically sound and contributes to the research field, assessed by the GLA-R-steering committee.
- The respective GLA-R-steering committee agrees upon the concept (during board meeting, or electronic communication). One member of the working party needs to act as bailsman of the project.
- The raw data remain within the academic network and no retraceable patient information will be provided to the cooperation partners.
- The research is sufficiently funded by the requesting entity and based on a formal agreement, which gives detailed information about scope, data usage, funding and presentation of the data.
- If presentations or publications arise from such co-operations, the GLA is represented adequately based on the relative distribution.

All these cooperative analyses will need approval of the WP/GLA-R-steering committee, as described under 7.1. A contract or appropriate agreement needs to be signed by the involved project partners.

7.2.3. Cooperation with legal entities

The GLA and the associated steering committee of the registry are open to cooperate with legal entities e.g. approval authorities or other relevant legal bodies, e.g. payers. For cooperation a regulatory framework will be used, to share data in an appropriate fashion as requested. However, the GLA reserves at any time the right to deny on the provision of data. If required, adoptions to the data base can be made to serve special requirements of distinct projects, if the costs of such are covered by the project costs.

All these cooperative analyses will need approval of the WP/GLA-R steering committee, as described under 7.1. A contract or appropriate agreement needs to be signed by the involved project partners.

7.3. Data Handling in projects

Aggregated data analysis is the preferred method of collaboration, exemptions can only be made upon presentation of sufficiently justifying reasons.

Patient level data will be provided only if indispensable for the project (double pseudonymized, e.g. Mainz-Liste, or appropriate tools.) and covered by respective informed consent and approval by relevant authorities.

In the case of cooperation with pharmaceutical companies a neutral third- party data provider must be involved for analysis, in case if single data sets are used for analysis.

8. Methods of the registry

8.1. Type of Investigation

Observational, non-interventional, pro- and retrospective patient registry.

8.1.1. Statement on investigational medical products

There will be no investigational medical products within the registry.

Neither is any treatment included into this protocol, nor will any advice be given for the treatment of an individual patient, based on data of the registry.

8.2. Database

The GLA-R will be implemented as a remote data entry system using an eCRF (electronic Case Report Form). After full implementation the entry portal, the eCRF will be the same for all centers and all lymphoma entities, with a harmonized data set used for all entities and additional specific data sets required for different lymphoma subtypes. Already actively recruiting registries (e.g. MCL, FL, MZL, T-NHL) will - in a first step - be co-affiliated with the GLA-R until integration into the GLA-R, established platform is feasible.

The database will allow to repeatedly access individual patient cases to expand the information available. After registering a patient, centers will receive regular reminders to fill in the appropriate information at least once yearly. Upon registration of a patient, data will be pseudonymized. If all data for an individual patient are entered (entry closed), data will be transferred to an anonymized mode. An appropriate tool will be used to identify potential double entries to avoid duplicates in the registry.

8.3. Data collection time points

In brief, data at baseline, at every treatment initiation, at the end of treatment and subsequent relapse and last follow-up (remission, death, reason for death) will be collected repeatedly.

Time points for the collection of data will be on the one hand event driven e.g. at the date of primary diagnosis, at any new therapy and in the case of death.

On the other hand, the clinical course of the patients will be followed for at least once a year. Centers will receive an annual reminder to fill the appropriate information in a time interval of max. 12 months.

8.4. Sample Size

There is no upper number of patients which can be included into the registry.

8.5. Data Collection (basic data set)

Information will be retrospectively collected during treatment until the moment of entry into the registry and prospectively thereafter. If acceptable by local and national regulations, the registry is open to integrate historical patient data, especially to provide a reasonable historical control.

Non-exclusive parameters are:

- Patient demographics, as age, sex, ethnicity
- Patient characteristics, as relevant concomitant diseases
- General performance parameters (e.g. ECOG)
- Disease characteristics, as histology, subtype, clinical and molecular risk factors
- Stage, subgroup-symptoms, risk group, including date of assessment
- Treatment characteristics, as e.g. Type of primary treatment: antibody, chemotherapy, HDT, use of novel agents, radiotherapy, use of maintenance, adherence
- Response to treatment: type of remission, DOR, PFS, OS after first-line treatment and subsequent lines, proportion of early relapses
- Method of disease evaluation
- Reasons for discontinuation of treatment
- MRD information if available and method of detection
- Pattern of relapse
- Type of subsequent treatment lines in the same way as for primary treatment
- Health care utilization, as hospital stays, use of certain drugs and methods (project-specific)
- Quality of life and late sequelae of treatment (project-specific)

The actual list of items collected are accessible in the internal section of the website of the GLA-R. Due to the nature of this registry, adoption of items will be required over time. In general, suggestions for revision submitted until 31.12. of each business year, will undergo review until 31.03. of the subsequent business year and if accepted will be integrated into the data base until 30.06. of the same year. The revised item list is published at the same time on the GLA-R website for reference. Dedicated questions for the conduct of scientific projects can be posed to the coordinating team of the GLA-R at any time.

8.5.1. Data for different lymphoma entities

As not all entities with dedicated data sets can be activated at the same time, the GLA will use a step by step strategy.

- First, in lack of a registry for large B-cell lymphomas this will be the first entity to be served in the upcoming registry.
- Second, stepwise all existing registries will be unified by prospectively collecting data on the respective populations and
- Integration of existing data upon clarification of rights and obligations

8.6. Documentation of adverse events

The registry, in contrast to interventional clinical trials, is not subject to the regulations of the current amendment of the AMG on the obligation to report. In principle, however, physicians in Germany are obliged to report adverse events according to § 6 of the professional code of conduct for physicians working in Germany. Reports are to be addressed alternatively to the Drug Commission of the German Medical Association (AKdÄ), the Federal Institute for Drugs and Medical Devices (Bundesinstitut für Arzneimittel und Medizinprodukte, BfArM), the Federal Institute for Vaccines and Biomedicines (Paul-Ehrlich Institut, PEI) or to the manufacturer by the participating site. Formal reporting to the AKdÄ or federal authorities must be carried out by the participating site and is not within the obligations of the GLA-R.

For the evaluation of applied therapy concepts within the registry, knowledge of serious adverse or unexpected events is useful. Hence, serious or unexpected adverse events should be collected on a project-specific basis. Serious events are events that

- Are fatal or life-threatening
- Require inpatient treatment or prolongation of inpatient treatment
- Result in permanent or serious disability or incapacity.
- Lead to a congenital anomaly or birth defect in a newborn/infant with maternal exposure to drugs.
- Represent—in the physician's opinion—a medically significant event, i.e., it could endanger the patient, require medical intervention or surgical intervention to prevent one of the events mentioned above.

In addition, adverse of special interest may be defined for specific disease situations, where current knowledge is limited and new information contribute to a better understanding of potential adverse events.

8.6.1. Adverse events in defined projects

If the GLA-R is part of a distinct research project of a GLA-member or a partner institution in which separate regulations are made for the documentation of adverse events, these regulations will only be followed for the respective project.

8.7. Duration of data collection

No formal end of the data collection is planned. As novel agents enter the therapeutic arena on a regular basis, and still a substantial number of patients die of lymphoma, the perpetuation of the registry is foreseen to evaluate the impact of novel developments. Therefore, last patient last data collection is not defined at this time point.

If there is no sufficient funding for the active conduct of the registry in the future, the collection of data and maintenance of the database might be paused. In this case, available data, will be anonymized and saved centrally in a GLA-owned storage tool in a format which allows further usage upon approval of the relevant committees. Funding of data migration and storage is guaranteed by the GLA. Until the data are secured by the GLA, the University of Mainz guarantees to securely store the data.

8.8. Registration of biological samples

In a first step, the registry is intended as a collection of clinical data. Whatsoever, sites will have the option to indicate whether biological materials are available for different patients (date, material). This information can be used to identify patients with suitable materials for research projects, after an additional and separate informed consent, independent from the registry.

In addition to this strategy, patients will be asked to donate samples which have been sent to a member of the reference pathology network, to make sparse material available for further usage within the GLA-network and to add results of reference pathology review to the data set of the GLA. If a donation is granted, samples will primarily be stored at the respective reference pathology. For the use of these materials based on a detailed project description, ethics applications and approval of the GLA-WP Biology needs to be obtained. Results need to be either integrated or available to the network after the publication of the data.

8.9. Biometry

In accordance with the underlying aims and questions of the registry, the following statistical analyses are performed on a routine basis.

First, a descriptive analysis of the different histological subtypes is performed. This includes, in addition to the frequency distribution of the subtypes, the distribution of demographic patient data, the diagnostics used in each case, treatment strategies, as well as their possible side effects and therapy results.

Frequency tables and graphical representations (in particular bar charts and box-and-whisker plots) are prepared to present the results. The descriptive analyses are supplemented by inferential statistical analyses. Appropriate statistical significance tests are used to examine whether systematic differences exist between the subtypes. Depending on the level of measurement and distribution of the target variables, appropriate hypothesis tests like Mann-Whitney-U-test, F-tests, Kruskal-Wallis tests, and Chi-squared tests are performed. All applied significance tests are performed at a two-sided significance level of 5 % and interpreted in an exploratory sense. Where appropriate, confidence intervals of important parameters are generated to the 95 % level. Time to event endpoints such as OS, PFS, DOR will be analyzed using the Kaplan-Meier method (and corresponding curves) (6). Where necessary, cumulative incidence—taking into account competing risks—will be obtained using the Aalen-Johansen estimator.

Within the scope of the registry, multivariate analyses, important target variables such as therapy outcome are modeled as a function of possible influencing variables. Logistic regression models are created for binary outcome measures such as the achievement of remission. Possible influencing variables are demographic and epidemiological data as well as the different applied therapy concepts. The strength of the influence of significant prognostic factors is quantified using the odds ratio (incl. 95 % confidence interval). Dependence of time to event endpoints on possible influencing variables will be assessed using the Cox-model regression model and suitable extensions (e.g. incorporating time-dependent covariates, time-varying effects of covariates etc.).

Specific research questions may require more sophisticated methods or even method development. This will be part of research proposals addressing such specific research questions.

8.10. Data Management

The GLA-R is using a certified and validated database. A detailed methodology for the data management in the GLA-R will be documented in a data management plan. The center will receive system documentation, training and support for the use of the eCRF. In case of new staff, the training can be performed by personnel of the center.

All data entries, modifications or deletions will be recorded automatically in an electronic audit trail indicating the individual subject, the original and new values, the reason for and time and date of change, as well as the person executing the change. The system will be secured to prevent unauthorized access to

the data or the system. Only people provided with a user ID and a password will be able to enter or change data.

Checks for plausibility, consistency and completeness of the data will be automatically performed during data entry. Based on these checks, queries will be produced. Centralized monitoring, where missing data or inconsistencies will be reported back to the respective center, complements this approach. Moreover a medical data review at certain intervals will help to identify erroneous and potentially unreliable data.

All data management activities will be done according to the current Standard Operating Procedures (SOPs) of the IZKS.

8.11. Quality and Risk Management

Data quality and risks to ensure data protection and reliability of registry results are continuously managed. The measures used will be proportionate to the inherent risks and the importance of the data collected.

If source data verification should become necessary for individual projects, on-site monitoring can be conducted. Details and the rationale for the chosen monitoring strategy will be specified in the monitoring plan. The center must allow the monitor to check all documents concerning the GLA-R and must provide support at all times to the monitor. Additionally to the on-site monitoring, remote monitoring visits could be conducted by the monitor. At the remote monitoring visits primarily administrative aspects and plausibility could be checked. Source data review and source data verification can only be conducted if the technical prerequisites are given and a valid regulatory approval exists.

9. Informed consent, ethics approval and data protection regulations

9.1. Ethics approval

For the GLA-R ethics approval will be obtained at the relevant committees of the participating centers. The process will be initiated at the site of the GLA-R Delegate.

9.2. Informed consent

Participation in this project is entirely voluntary. There is no direct impact on the treatment of the individual patient. The GLA-R informed consent form will be distributed to patients eligible for this registry and still alive. In addition, patients will receive all relevant information on data protection in its latest version and the potential use of their data for the different analyses, including shared analyses with network partners and commercial cooperators.

Historical patient data will be entered if appropriate consent exists by hospital and/or ethic regulations.

The informed consent to participate in the registry may be withdrawn by the patient verbally or in written form at any time during the trial. The patient must not entail any disadvantage therefor or be coerced or unduly influenced to continue to participate. Furthermore, the patient is not obligated to disclose reasons for the withdrawal of the consent.

9.3. Data protection

Within the registry, the applicable data protection is respected. The EU Regulation 2016/679 of the European Parliament and the Council GDPR, which has been in force in Germany since May 2018, defines various legal aspects of data protection. According to Article 6(1) (a), the processing of personal data is permitted if "the data subject has given his or her consent to the processing of personal data for one or more purposes". Article 5(1) (b) also states that "personal data may be used only for specified, explicit and legitimate purposes and may not be used for other purposes not agreed upon; the further use of data intended for archives in the public interest, for scientific or historical research projects or for statistical purposes is not incompatible with the original purposes pursuant to Article 89(1)". Article 7(1) further states that "if the use of the data is based on consent, the person responsible must prove that the individual concerned has given consent to the use of personal data".

In order to comply with the provisions of the GDPR, the collection of data in the registry is only possible if written consent has been obtained from the patient, if not addressed in special regulations (e.g. deceased patients).

If consent is given, the collected data are entered into an access-protected database. This database does not contain any information that allows clinical data to be assigned to an individual person. Instead, all data are assigned to a clearly defined alphanumeric pseudonym that contains neither parts of the name nor the date of birth.

9.4. Data Protection regulations

Data protection regulations in their latest version will be followed at any time, including withdrawal and consent and the right of deletion of data.

The patient is entitled to withdraw his informed consent to the collection, storage and transfer of his patient data at any time. Depending on the patient's declaration, the data collected so far can either be corrected, updated or made anonymous. A withdrawal of the informed consent does not affect the lawfulness of the data processing carried out until the withdrawal (Article 7 paragraph 3 GDPR).

9.5. Trusted third party

Patient identifying data (e.g. surname, first name, date of birth and address) will be collected and stored separated of the medical data in the trusted third part in safe custody. There will be an organizational separation from other registry operations. Only trained and authorized personnel will have access to the personal identifying data. The disclosure to any third party is excluded.

10. Data reports

A summary report of the clinical data of the registry is prepared annually. The following analysis will be performed by the institution to which the conduct of the registry will be delegated on behalf of the GLA.

- Number of patients included into the registry and in the different lymphoma subtypes
- Patient characteristics
- Cumulative entity overall survival, depending on age, sex

Each center has the option to receive the data of their own patients entered on a per center analysis (with and without benchmark data). All members of the registry have access to e.g. the annual analyses and other appropriate materials. If used, the GLA-R needs to be referenced.

Note: As of 2023 IZKS/IMBEI Mainz are responsible for the provision of the annual analysis.

For each lymphoma entity-specific data points or research questions may be predefined which will be specific to the respective part of the GLA-registry. The basis for these data points will be revised annually by the speakers of the respective working parties to keep the data base updated for the most recent development. Changes to the item list will be reported on the website of the society. Reminders will be sent by the project coordination in summer of the preceding year, to be discussed at the annual meeting and then to be integrated into a regular database release in Q1 or Q2 of the subsequent year.

Primary data analyses will be provided in Q2 to the WP for discussion and distribution, in general for presentation at the annual meeting.

11. Role of funding sources

There is no single funding source to cover the costs of the registry. For the start of the project the GLA e. V. provides funding to establish the data base and facilitate registry coordination and management. In addition, cooperation projects with industrial partners have been defined to cover remaining project costs. As of Q1 2023 funding for the first 3 years is covered.

The GLA is planning to conduct the registry as a long-term project. Therefore, during the set-up phase of the registry additional applications for future funding (2026 - 2030) will be made from a variety of funding sources such as:

- GLA funding
- Public funding (German Cancer Aid, foundations, payers such as GBA, IQWiG)
- Restricted funding for defined research projects (industrial partners)
- Individual grants for studies within the registry (GLA-members)

12. Disease specific Registries

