POD12	Progression of disease within 12 month
POD24	Progression of disease within 24 month
PR	Partial response
PTLD	Post-transplant lymphoproliferative disorder
QoL	Quality of life
RKI	Robert Koch Institute
SC	Steering committee
SCT	Hematopoietic stem cell transplantation

SD	Stable disease
SOP	Standard operating procedure
T-NHL	T-cell non-Hodgkin lymphoma
WHO	World health organization
WP	Working Party

1. Overall Background

Real world evidence has become a widely accepted source of information for various cancer entities to add to or partly substitute the result from controlled clinical trials. In detail, real world data collections provide information on therapeutic pathways, use of novel treatments, treatment algorithms and impact of these therapies on the overall/more general patient population (1, 2). Special benefits are the long-term collection of data over the entire disease course and the integration of information of literally all patients without inherent limitations of controlled trials. In addition, long-term collections allow understanding of the change of treatment patterns over time, survival trends in different patient generations, trends in participation in clinical trials and their impact on survival, quality of life (QoL), health care utilization and potentially complications and limitations of multiple treatments (3).

In this intent, the German Lymphoma Alliance will establish a clinical, non-interventional, retro- and prospective clinical registry. All patients with malignant lymphatic malignancies (except chronic lymphocytic leukemia (CLL), morbus hodgkin (MH) and multiple myelom (MM)) and related lymphoproliferative diseases can be included into the registry.

The current lymphoma landscape - the impact of Real World Evidence

Major improvements of biological understanding and classification of malignant lymphomas has been made over the last decades. This has resulted in a continuous fragmentation of disease entities with increasingly smaller samples sizes, which in turn limits the chance to study all entities prospectively in distinct trials.

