12.2.2. Scientific rationale

Mantle cell lymphoma is a rare subtype of malignant B-cell-lymphomas with a generally aggressive disease course and poor prognosis. In recent years biological understanding of the pathophysiology of the disease has markedly increased and thereby prognostic stratification could be established. The improved understanding led to the identification variety of potential molecular treatment targets and development of specific drugs, which have improved current treatment results. Still, most patients continue to develop refractory disease and die due to the underlying lymphoma. Therefore, there is still a high need for improved understanding and better treatments.

Due to the nature of clinical research in phase I–III, most trials focus on the results of specific treatment lines and cannot provide an overview of the entire disease course, which is necessary to answer many unsolved questions as described above. To overcome the issue of lacking data from prospective data on the entire disease course of patients, only data from a registry are able to provide the information needed and close the current gap in knowledge. Furthermore, in contrast to data available from prospective clinical trials, the collection of data over the entire disease course helps to understand the change of treatment patterns, complications of the disease and multiple treatments and allows for the comparison of survival of different patient generations.

Non-exclusive examples of specific questions to be addressed from registry data are: fate of indolent NHL, course of primarily extranodal MCL, impact of high risk characteristics and influence of treatment selection on the results of the following treatment line.

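### The annual report's only survival item splits overall survival by entity, age and sex but not by diagnosis period, although the registry plans to combine patients from different eras

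*Protocol*

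**What the plan says.** Section 10 states that "A summary report of the clinical data of the registry is prepared annually" and lists three items: patient numbers by subtype, patient characteristics, and "Cumulative entity overall survival, depending on age, sex". The third is the only survival item. It names entity, age and sex, and neither diagnosis period nor data source.

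Mixing of eras is planned. Section 6.3 foresees migration of the existing lymphoma registries and, after regulatory clearance, of data from former trial groups. Section 8.5 adds that, where regulations permit, "the registry is open to integrate historical patient data, especially to provide a reasonable historical control". Section 2 wants earlier-trial data as a benchmark.

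Comparison over time is a stated purpose. Section 1 counts "survival trends in different patient generations" among what long-term collection makes understandable, and Section 12.2.2 says of mantle cell lymphoma that such collection "allows for the comparison of survival of different patient generations".

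Other survival work is also foreseen. Section 8.9 says "the following statistical analyses are performed on a routine basis", and these include "Time to event endpoints such as OS, PFS, DOR will be analyzed using the Kaplan-Meier method" as well as Cox regression. Section 5 names period of treatment as a subgroup for treatment pathways and adds an open list of exploratory subgroup analyses. No section specifies survival by calendar period.

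**The concern.** Section 10 itself chooses the breakdowns of a recurring report and leaves out the one that this registry's data structure makes most important. Patients diagnosed from 2023 have short follow-up, and imported patients have long follow-up. In one Kaplan-Meier curve the early part mixes both groups and the late part comes from the earlier patients alone. Censoring is then related to era. If survival also differs by era, censoring is informative for the pooled curve.

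Three things follow if the item is run without a period split. Long-term survival in the report reflects earlier treatment more than present care. The figure can move in the year a legacy data set is loaded, with no change in outcome. And the report does not show the comparison of patient generations that the protocol gives as a reason for the registry. None of this depends on how the imported patients were selected: it remains even if all of them were routine-care patients followed from diagnosis.

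**Working it through.** The protocol states no survival figure or import number here, so there is nothing to reproduce. The calculation below only illustrates size.

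**Inputs**
- From the protocol (Section 12.1.5): 500 large B-cell lymphoma patients per year for 3 years, so 3 × 500 = 1500 new patients.
- Assumed: new patients enter at diagnosis, uniformly over 3 years, with data cut at the end of that time. Their 5-year survival is 65%.
- Assumed: 500, 1000 or 2000 legacy patients, all followed for at least 5 years, with 5-year survival of 50%, 55%, 60% or 65%.
- Assumed: exponential survival in each group.

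**Formulas**
- Hazard λ = −ln(S₅)/5. New: −ln(0.65)/5 = 0.0862 per year. Legacy: 0.1386 (50%), 0.1196 (55%), 0.1022 (60%), 0.0862 (65%).
- Numbers at risk: R_old(t) = N_old·exp(−λ_old·t). R_new(t) = 1500·(1 − t/3)·exp(−λ_new·t) up to 3 years, then zero.
- Pooled hazard h(t) = [R_old·λ_old + R_new·λ_new]/[R_old + R_new], and pooled S(t) = exp(−∫h), integrated numerically.

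**Example: 500 legacy patients, 5-year survival 50%.** Integration to 3 years gives S(3) = 72.0%. From then on only legacy patients are at risk, so S(5) = 0.720 × exp(−2 × 0.1386) = 0.720 × 0.758 = 54.6%. The true figure for new patients is 65%. The size-weighted average of the two cohorts would be (500 × 50% + 1500 × 65%)/2000 = 61.3%, so the pooled curve lies below even the mixture that it appears to describe.

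**Pooled 5-year survival**

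| Legacy 5-year survival | Legacy n = 500 | n = 1000 | n = 2000 | Points below 65% |
|---|---|---|---|---|
| 50% | 54.6% | 53.3% | 52.1% | 10.4–12.9 |
| 55% | 58.1% | 57.2% | 56.5% | 6.9–8.5 |
| 60% | 61.6% | 61.1% | 60.7% | 3.4–4.3 |
| 65% | 65.0% | 65.0% | 65.0% | 0 |

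At 2 years, where both groups contribute, the shift is smaller. With legacy survival of 50% the pooled figure is 81.3%, 79.9% and 78.5%, against a true 84.2% for new patients.

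**Does it fade with time?** A second set of assumptions continues 500 new patients per year to a 2029 cut and adds 300 to 3000 legacy patients diagnosed 2005–2018, with 5-year survival of 55% (legacy) and 65% (new). Legacy patients are then 33–83% of those at risk at 5 years, and the pooled 5-year figure is 63.3–58.5%. The distortion at 5 years shrinks but does not vanish. At 8 years all patients at risk are still legacy patients.

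**The case against.** A reader might infer four stronger things that the protocol does not support.

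- *That this is the registry's only standing survival output.* Section 8.9 makes Kaplan-Meier and Cox analyses routine. The statement is true only of the list in Section 10.
- *That the protocol has decided to pool all diagnosis years.* It does not say so. The word cumulative may mean no more than the survival function, and the item excludes no further breakdown. The use of historical data as a control (Section 8.5), as a benchmark (Section 2), and for comparison over time in HIV-associated lymphoma (Section 12.3.3) points towards keeping eras apart.
- *That trends cannot be studied.* Date of primary diagnosis is a collection point (Section 8.3), the subgroup list in Section 5 is open, and period could enter a Cox model or a separate project.
- *That imported patients will dominate by a known amount.* Imports depend on consent and clearance, and their size is not given. Large B-cell lymphoma has no existing registry (Section 8.5.1), so its legacy patients would have to come from former trials or historical entries. The follicular registry (950 patients since May 2020) and the T-cell registry (nearly 300 since 2021) are recent. Of about 1400 patients in the European mantle cell registry, only the German ones are to move. A distortion in one entity does not carry over to another.

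Nor does the protocol name a 5-year figure or say that the report will be read as current care. The gap of 15 points behind the largest shift is an assumption. Report strata are also often left to an analysis plan, which is not shown.

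All of this limits the claim. What remains is that Section 10 itself sets the breakdowns and omits period, and that neither Section 8.9 nor Section 5 names period for survival. A historical control serves its purpose only if it is kept separate from the patients compared with it.

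**Conclusion.** The point holds as a gap in the specification of the annual report. Run as listed, late survival estimates would rest on earlier-diagnosed patients, and the pooled curve would be biased for current care whenever survival has changed. Sections 12.2.2 and 12.3.2 describe improved results in mantle cell and HIV-associated lymphoma, so a downward bias is the plausible direction there.

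In the illustration the 5-year figure is about 3–4 points low for a 5-point difference between eras, 7–9 for 10 points, 10–13 for 15 points, and unbiased for none. These sizes rest on assumed legacy numbers and survival, exponential curves, and new patients enrolled at diagnosis. Section 3 admits patients at any point in the disease course, so some patients enrolled from 2023 will have been diagnosed earlier. That is a further reason to split by diagnosis date and not by enrolment date. The point is modest, but the correction is cheap and serves purposes that the protocol states.

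**What to change.** In Section 10, change the survival item to: *overall survival by entity and diagnosis period, by age and sex, each curve shown only as far as that period has patients at risk*. Bands of about five years would be workable. Naming the data source alongside the period would also make the effect of an import visible.

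The date of diagnosis is already collected (Section 8.3), so no new data item is needed. The cost is one changed line, a stratified run each year, and wider intervals within each period, most noticeably in rare entities, where age and sex may have to be coarsened. The most recent period will have no long-term estimate at first, which is an accurate statement of what the data can show. Period analysis, using person-time in a recent calendar window, could supply an up-to-date long-term figure but is optional.
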